## 8.0 CLINICAL MANAGEMENT ISSUES

### 8.1 Clinical Management Issues

The IMPRESS study will use the Division of AIDS Table for Grading the Severity of Adult and Paediatric Adverse Events (DAIDS AE Grading Table) Version 1.0, December 2004 (Clarification, August 2009)

- Patients need to be assessed for evidence of musculoskeletal toxicity at every study visit through history taking and physical examination.
- Ocular toxicity will be assessed using the Snellen and Ishihara tests at baseline and month 2 and/or when clinically required (Control Arm only). Patients will be educated about symptoms of ocular toxicity before treatment initiation, and will be assessed for ocular toxicity for the duration of TB therapy when Ethambutol forms part of the TB regimen. The Snellen and Ishihara tests will be repeated if any symptoms of ocular toxicity or any change in vision occurs.

- All patients will undergo ECG monitoring at baseline, Month 2, Month 4, Month 6 (and 2 monthly whilst being administered with Moxifloxacin). This will be repeated if patients complain of chest pain or syncope. Moxifloxacin will be substituted for Ethambutol if there is evidence of QT prolongation, or if patients QRS complexes change in amplitude from baseline.
- Patients must not have evidence of severe or life-threatening liver disease at baseline (Bilirubin, AST and ALT < 5 times the ULN), no evidence of renal impairment i.e. creatinine clearance of > 60 mls/min, serum potassium of > 3.0 mmol/l.

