## SCHEMA

**Design:** This is an open label randomized controlled clinical trial comparing two regimens for treatment of smear-positive pulmonary TB, among patients previously treated for TB. The primary objective is to determine if a Moxifloxacin-containing regimen, substituting Moxifloxacin for Ethambutol, of 24 weeks duration is superior to a control regimen of 24 weeks duration in improving treatment outcomes in patients with recurrent TB.

**Duration :** Intervention Arm : Approximately 6 months treatment + 12 months post treatment follow up

Control Arm : Approximately 6 months treatment + 12 months post treatment follow up

**Sample Size:** 330

**Population :** This study will include adults 18 years and over with a previous history of TB. HIV infected and uninfected patients will be included in the study as well as patients on ARVs provided that these are not contra-indicated with any of the study drugs. Patients with *M tuberculosis* resistance to Rifampicin will be excluded at screening using Gene Xpert technology.

**Randomization:** Patients will be randomized to receive 1 of 2 TB retreatment regimens

[figure not shown]

Figure 1 : IMPRESS patient screening and randomization arms

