### 1.3 Rationale for Moxifloxacin

Moxifloxacin is an 8-methoxyquinolone compound. Several studies have demonstrated that Moxifloxacin is an effective treatment against TB and has potential to shorten the course of TB treatment. In, 2003, a randomized controlled trial in Tanzania measured the bactericidal activity of Moxifloxacin in patients with Pulmonary TB (PTB). The study compared 3 groups of pulmonary TB patients. Group 1 received Isoniazid, Group 2 received Rifampicin and Group 3 received Moxifloxacin. Patients completed 5 days of monotherapy and sputum samples were collected before treatment was started and then daily for the duration of treatment. Early bactericidal activity (EBA) was measured as time taken to kill 50% of viable bacilli and the decrease in sputum viable count. The average time to bactericidal activity of Moxifloxacin was 0.88 days and the mean EBA was 0.53. For Isoniazid and Rifampicin the mean EBA was 0.77 and 0.71 respectively. The study concluded that Moxifloxacin is highly bactericidal with similar activity to Rifampicin in human patients. Gillespie *et al* (1999), tested Moxifloxacin activity against 4 other quinolones against an array of clinical isolates of mycobacteria. When compared with other quinolones; Moxifloxacin had a lower MIC against *Mycobacterium tuberculosis* than Ciprofloxacin, Levofloxacin, Sparfloxacin and Isoniazid.

In terms of its safety profile, Moxifloxacin is well tolerated. Two randomized controlled trials assessed the effectiveness and safety of Moxifloxacin. Nausea is the most common side effect associated with Moxifloxacin however, very rarely does this result in drug discontinuation.

In a Phase II randomized controlled trial which substituted Moxifloxacin with Ethambutol, it was determined that Moxifloxacin is well tolerated and resulted in a higher frequency of negative cultures in earlier time points among patients with smear positive pulmonary tuberculosis. This was an important study as it demonstrated that Moxifloxacin is a suitable substitute for Ethambutol.

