## **2.0 STUDY AIMS AND OBJECTIVES**

### **2.1 Primary objective**

The primary objective is to determine if a Moxifloxacin-containing regimen, [Isoniazid (H), Rifampicin (R), Pyrazinamide (Z), Moxifloxacin (M)], substituting Moxifloxacin for Ethambutol, of 24 weeks duration is superior to a control regimen [Isoniazid (H), Rifampicin(R), Pyrazinamide (Z), Ethambutol (E)] of 24 weeks duration in improving treatment outcomes in patients with recurrent TB.

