### 3.0 STUDY DESIGN AND SETTING

This is an open label randomized controlled clinical trial comparing two regimens for treatment of smear-positive pulmonary TB, among patients previously treated for TB. Patients will be randomized to receive one of the two TB retreatment regimens as listed below. In the Intervention Arm, Moxifloxacin will be substituted for Ethambutol. “Study drugs” refer to all the drugs listed in Table 1.

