**Table 4: Possible adverse effects and drug interactions.**

Study Drug	Adverse effects	Drug interactions	Comments
Rifampicin	Gastro-intestinal: nausea, anorexia, mild abdominal pain, diarrhea. Cutaneous reactions: mild flushing and pruritus. Hepatitis especially if alcoholic or history of liver disease.	Efavirenz, nevirapine, protease inhibitors. Rif is an enzyme inducer and increases metabolism of oral anticoagulants (warfarin), oral diabetic drugs, digoxin, phenobarbitone and other anti-epileptics.	Colours urine, sweat and tears orange-pink.

	Serious: flu-like syndrome and shock		
Isoniazid	Peripheral neuropathy, hepatitis (mostly in those > 35yrs), generalized skin rash, fever, joint pains – rare.	Inhibits metabolism of anti-epileptics.	
Ethambutol	Progressive loss of vision caused by retrobulbar neuritis, usually manifests first as loss of colour vision and usually presents after the client has been on treatment for at least two months. This is usually caused by excessive doses of Ethambutol. Skin rash, joint pain, peripheral neuropathy.	There are no known drug–drug interactions involving Ethambutol.	Do not administer if optic neuritis present.
Pyrazinamide	Liver damage: anorexia, mild fever, tender enlargement of the liver and spleen may be followed by jaundice. Arthralgia: This is common and mild. The pain affects both large and small joints, the level of uric acid is increased and gout may occur. Skin rash on sun exposed areas.	Low potential for drug interactions.	
Moxifloxacin	Prolonged QT interval, well tolerated – low rates of gastrointestinal adverse effects.	Potential interaction: Rifampicin, iron/iron containing supplements, aluminium/magnesium containing antacids, zinc/zinc containing supplements, didanosine, sucralfate.	

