## 8.4 Reporting Serious Adverse Events (SAEs)

The following Serious Adverse Event will be reportable to the database and regulatory authorities: AE's that:

- Results in death
- Is immediately life threatening at the time of occurrence
- Results in persistent or significant disability or incapacity
- Requires in-patient hospitalization or prolongs hospitalization
- Results in a congenital anomaly or birth defect
- Is deemed an "important medical event" by the Investigator (may not be immediately life threatening or result in death or hospitalization but may jeopardize the patient e.g. convulsions. This will include any adverse event that *is unexpected, but related* to the study product, e.g. asymptomatic prolonged QT interval associated with Moxifloxacin.

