### QTc Prolongation

Participants in this trial may receive Moxifloxacin which has the potential to prolong the QTc interval. All QTc measurements will be corrected with the Fridericia correction.

The protocol-specific criteria for grading prolonged QTc are as follows:

PARAMETER	GRADE 1 MILD	GRADE 2 MODERATE	GRADE 3 SEVERE	GRADE 4 POTENTIALLY LIFE- THREATENING
Prolonged QTc (using Fridericia QT correction formula)	Asymptomatic, QTc interval 0.45 – 0.47 sec	Asymptomatic, QTc interval > 0.47- < 0.50 sec	Asymptomatic, QTc interval $\geq$ 0.50 sec OR a QTc > 0.48 sec with an increase in interval $\geq$ 0.06 sec above baseline	Life threatening consequence, eg, Torsade de pointes or other associated serious ventricular dysrhythmia

If Grade 2 QTc prolongation develops during the course of the study and is felt to be due to study medications, the participant will be monitored more closely, with twice weekly visits and QTc evaluation. If Grade 3 QTc prolongation occurs, all study drugs will be discontinued and the participant will be referred to hospital for further assessment and management. If the QTc prolongation is considered most likely to be due to concomitant illness or medication, standard management, including discontinuation of the likely causative agent, should be undertaken.

If a participant develops Grade 4 QTc prolongation, he or she will be hospitalized and discontinued from study medications. If the prolongation is felt to be caused by a concomitant medication and resolves with discontinuation of that agent, study medications may be restarted. Otherwise, the participant will be referred to the NTP for treatment of his or her TB according to local standards of care. The participant will continue to be followed on study, off study drugs.

Serious adverse events will be reported to the MCC and the UKZN Biomedical Research Ethics Committee. (BREC) according to their specific requirements.

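### Protocol 8.1 states its response to QT prolongation backwards, and reversing the words alone would still leave it at odds with Section 8.5 at QTc Grades 3 and 4

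*Protocol*

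**What the plan says.** Protocol 8.1 sets the ECG schedule for all patients (baseline, Months 2, 4 and 6, and a repeat for chest pain or syncope). It then gives the response: "Moxifloxacin will be substituted for Ethambutol if there is evidence of QT prolongation, or if patients QRS complexes change in amplitude from baseline". It names no QTc grade, gives no size for the QRS change, and does not refer to Section 8.5.

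The same form of words appears where the experimental regimen is described:
- Schema: "substituting Moxifloxacin for Ethambutol, of 24 weeks duration is superior to a control regimen of 24 weeks duration"
- Section 2.1: "Pyrazinamide (Z), Moxifloxacin (M)], substituting Moxifloxacin for Ethambutol"
- Section 3.0: "In the Intervention Arm, Moxifloxacin will be substituted for Ethambutol"

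Three places tie QT prolongation to moxifloxacin:
- Table 4, moxifloxacin row: "Prolonged QT interval, well tolerated"
- Section 8.4, as an example of a reportable event: "asymptomatic prolonged QT interval associated with Moxifloxacin"
- Section 8.5, under QTc Prolongation: "Participants in this trial may receive Moxifloxacin which has the potential to prolong the QTc interval"

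Section 8.5 grades QTc from 1 to 4 by the Fridericia correction and sets its own actions for Grades 2 to 4. Section 8.2.5 counts ethambutol among the study drugs.

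**The concern.** Section 8.1 is where a clinician reading an ECG would look for what to do. Taken in the sense the protocol uses elsewhere, its sentence tells that clinician to start the QT-prolonging drug in a patient whose QT is already long. It also says nothing for patients who are taking moxifloxacin.

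The obvious repair is to swap the two drug names, but that leaves a second problem. Section 8.5 already has a graded response that stops treatment altogether at the higher grades. Nothing says which section prevails.

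What is at stake is patient safety at the point of care, not the estimate of the treatment effect.

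**Working it through.** No sample size, power or event figure is involved, so the check sets the texts side by side.

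**1. Direction.** In the Schema, Section 2.1 and Section 3.0 the phrase means moxifloxacin in, ethambutol out. Section 8.1 uses the same construction. The ethambutol row of Table 4 lists visual loss, rash, joint pain and neuropathy, with no QT effect. The instruction therefore gives the drug with the QT risk and removes one without it. Section 1.3 describes a trial that "substituted Moxifloxacin with Ethambutol" while citing it as evidence that moxifloxacin can replace ethambutol. The protocol thus handles this verb loosely elsewhere, which makes a slip the likely cause.

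**2. Reach of the literal text.** Table 1 gives four arm-by-phase regimens: HRZM, HRM, HRZE and HR.
- Ethambutol is in 1 of 4 (HRZE, control intensive phase), so the instruction can act only there.
- Moxifloxacin is in 2 of 4 (HRZM and HRM). Those patients get no action from the sentence.
- For control patients, the scheduled ECGs that could matter are baseline, just before ethambutol starts, and Month 2, when on-schedule patients move to HR. Symptom-driven repeats and an extended intensive phase add some further opportunity.

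**3. Direction reversed, compared with Section 8.5.** Suppose the sentence read that ethambutol replaces moxifloxacin.

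| QTc grade | Reversed 8.1 | Section 8.5 | Compatible? |
|---|---|---|---|
| 1 (0.45–0.47 s) | Swap one drug | No QTc-specific action; 8.3.1 generally continues drugs | Mild tension |
| 2 (>0.47 to <0.50 s) | Swap one drug | Twice-weekly visits and QTc checks if attributed to study medication; 8.3.2 continues drugs unless judged unsafe | Mild tension |
| 3 (≥0.50 s, or >0.48 s with a rise ≥0.06 s) | Swap one drug | Stop every study drug, refer to hospital | Conflict in the immediate action |
| 4 (life-threatening) | Swap one drug | Admit, stop study medications; NTP takes over unless a concomitant medication was the cause and the event resolves | Conflict |

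The replacement drug is itself a study drug, so it falls under the Section 8.5 stop. In the intensive phase a patient would be on 4 drugs (HRZE) under the reversed sentence and on 0 under Section 8.5. In the continuation phase the count under the reversed sentence is 3 (HRE) if ethambutol is carried on, or 2 (HR) if the control regimen is followed. The protocol does not say which. Section 8.5 again gives 0.

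The stop sentences at Grades 3 and 4 do not depend on attribution to study drugs. Section 8.5 does allow standard management when a concomitant illness or medication is the likely cause. Section 8.1 has no such exception.

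**4. QRS trigger.** Any change in amplitude from baseline sets off the same response. No size, lead or direction is given in 8.1, and no other section supplies one.

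**The case against.** The strongest reply is that nobody would be misled. The intended direction is plain to any clinician, Section 8.5 is the more specific text, and it opens by naming moxifloxacin as the risk. Section 8.2.4 and the section on discontinuation of study treatment let the investigator withdraw drugs in any case. Much of this stands. It means that moxifloxacin patients are already protected at Grades 2 to 4, and Section 8.3.1 covers Grade 1. A reader might infer that these patients have no QT safeguard, and the documents do not support that.

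A second reply is that the conflict with Section 8.5 tests a sentence the protocol does not contain, and that 8.1 gives no timing. At Grade 3 this has force. Section 8.3.3 leaves later TB treatment to the clinician, so a stop, a referral and then a regimen with ethambutol could be read in sequence. A reader might conclude that the two rules can never both be followed at Grade 3. The text supports only a clash in the immediate action. Grade 4 is firmer, because Section 8.5 passes the patient to the NTP unless a concomitant medication was the cause.

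A third reply is that Section 8.5 needs no QRS rule, since that part concerns QTc. That is fair. The gap is the missing threshold in 8.1, not the missing counterpart in 8.5.

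None of these replies makes the sentence right. Clinical sense may recover the direction, but it does not supply the grade at which a swap applies, the order of precedence, or a QRS cut-off.

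**Conclusion.** The sentence in Protocol 8.1 is wrong as written and should be removed or corrected. It is almost certainly a slip, and its literal reach is limited to control patients taking or about to take ethambutol (1 of 4 arm-by-phase regimens). Reversing the drug names would leave a firm conflict with Section 8.5 at Grade 4, a conflict of immediate action at Grade 3, and a QRS trigger that cannot be applied consistently.

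This rests on reading the substitution phrase as the Schema and Sections 2.1 and 3.0 use it. The counts above are counts of text categories and do not measure risk. The documents give no QT event rate, so no number of patients is claimed.

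A reader might infer that the slip sends control patients across to moxifloxacin and so contaminates the comparison. The documents do not support that. The literal reach is narrow, staff would probably not act on the reversed wording, and SAP Section 4 bases the primary analysis on the intention-to-treat principle. This is a patient-safety wording correction, and the trial's conclusions are unaffected.

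**What to change.** **Preferred.** Delete the sentence from Section 8.1, including the QRS-amplitude trigger, and replace it with a reference to the QTc grades and actions in Section 8.5.

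**If the sponsor wants to keep a swap.** Reword it so that ethambutol replaces moxifloxacin. Limit it either to a named QTc grade below Grade 3 or to the period after a Section 8.5 stop. State that Section 8.5 prevails. Define the QRS change that counts, or drop it. The clinical thresholds are for the sponsor to set.

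New Grade 1 rules, rules for symptomatic prolongation below Grade 3, ethambutol dose and supply details, and added vision tests are not part of the required correction.

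**Cost.** One protocol clarification, which Section 10.6 requires the ethics committee and the regulator to approve before it is used. The preferred option changes neither the sample size, the visit schedule nor the SAP.

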**Table 1: Study Regimens**

Study Regimens		
	Intensive phase	Continuation phase
Intervention Arm *	HRZM daily (first 2 months )	HRM daily (4 months)
Control Arm **	HRZE daily (first 2 months )	HR daily (4 months )

H – Isoniazid; R – Rifampicin; Z – pyrazinamide; E – Ethambutol; M - Moxifloxacin

\* When patients become smear negative, they will be switched from the intensive phase to continuation phase with Isoniazid, Rifampicin and Moxifloxacin for 4 months

\*\*When patients become smear negative, they will be switched from the intensive phase to continuation phase with RIF and INH for 4 months.

In this study the total duration of TB therapy will be 24 weeks (6 months) for the Intervention Arm, and the Control Arm. The duration of TB treatment may increase due to a delay in the time to sputum conversion. This will result in the extension of TB treatment beyond 6 months.

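### Protocol 8.1 reverses the drugs in its QT action; read as intended, it conflicts with the Grade 3 and 4 stops in 8.5, whose QTc grades also leave a narrow gap for symptomatic patients

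*Protocol*

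**What the plan says.** Protocol 8.1 (Clinical Management Issues) sets out ECG monitoring and the response to it. "All patients will undergo ECG monitoring at baseline, Month 2, Month 4, Month 6", so both arms are covered. On an unscheduled ECG it adds: "This will be repeated if patients complain of chest pain or syncope". The action is "Moxifloxacin will be substituted for Ethambutol if there is evidence of QT prolongation", with a second trigger in the same sentence: "or if patients QRS complexes change in amplitude from baseline". No grade is named.

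The same verb defines the trial's comparison. Section 3.0 states: "In the Intervention Arm, Moxifloxacin will be substituted for Ethambutol". The primary objective in 2.1 describes the intervention as "substituting Moxifloxacin for Ethambutol, of 24 weeks duration is superior to a control regimen". In both places moxifloxacin goes in and ethambutol comes out.

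Protocol 8.5 (Safety Monitoring, under QTc Prolongation) names moxifloxacin as a drug that can lengthen QTc and gives its own grading table and actions:

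- Grade 2, if attributed to study medication: closer monitoring, with visits and QTc checks twice a week.
- Grade 3: all study drugs stopped and referral to hospital.
- Grade 4: admission and study medications stopped.
- If another illness or drug is the more likely cause, standard management applies.

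Sections 3.0 and 8.2.5 both count ethambutol as a study drug.

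**The concern.** A safety instruction that names the wrong drug to give should not stand, even where staff would probably guess the meaning. Correcting the word order then exposes a second difficulty. When QTc prolongation reaches Grade 3 or 4 and is attributed to study drug, 8.1 tells staff to swap moxifloxacin for ethambutol and carry on, while 8.5 tells them to stop treatment. A clinician cannot do both, and nothing in the protocol says which section prevails.

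The 8.5 table adds a smaller problem. Grades 1 and 2, and the part of Grade 3 based on QTc of 0.50 s or more, apply only to patients without symptoms. Yet 8.1 orders a repeat ECG precisely when a patient reports chest pain or syncope. The patients most likely to have an unscheduled ECG are therefore those the table grades least clearly.

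What is at stake is consistent handling of a known moxifloxacin risk. The primary analysis is not affected.

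**Working it through.** The plan gives no numerical figure to reproduce here. The check sets the texts side by side and works the grading rule through.

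**Step 1: the literal reading of 8.1.** It can act only where a patient is taking ethambutol. Table 1 gives the Intervention Arm none. Control Arm patients take it in the intensive phase and are then "switched from the intensive phase to continuation phase with RIF and INH for 4 months". By Table 2 that phase is 56 of 56 + 112 = 168 doses, or 8 of 24 weeks (longer if sputum conversion is delayed). With 330 patients randomised 1:1 (SAP 2), 330/2 = 165 are in the Control Arm. Of the three scheduled on-treatment ECGs (Months 2, 4 and 6), only Month 2 normally falls in that window; unscheduled ECGs could also do so.

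**Step 2: the intended reading against 8.5.** Here the population is the other 165 patients, on moxifloxacin for 24 weeks, with all three on-treatment ECGs.

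| QTc grade | 8.1 as intended | 8.5 | Compatible? |
|---|---|---|---|
| 1 | Replace moxifloxacin with ethambutol | No action stated | Yes |
| 2 | Same | Closer monitoring | Yes; the switch is an added step |
| 3 | Same | Stop all study drugs, refer to hospital | No |
| 4 | Same | Admit, stop study medications | No |

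The conflict is at 2 of 4 grades. At both, moxifloxacin is removed under either text. The disagreement is over the companion drugs and ethambutol.

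**Step 3: the grading gap.** Grade 3 in 8.5 has two limbs: asymptomatic with QTc of 0.50 s or more; or QTc above 0.48 s with a rise of at least 0.06 s from baseline. Grade 4 needs a life-threatening consequence. Take a symptomatic patient with no such event.

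- The first limb fails because of the symptoms, as do Grades 1 and 2.
- The second limb fails whenever the rise is below 0.06 s, whichever way its scope is read.
- The ungraded range at or above 0.50 s is therefore 0.50 s up to, but not including, baseline + 0.06 s. It is non-empty only if baseline > 0.50 − 0.06 = 0.44 s.

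| Baseline QTc (s) | Baseline + 0.06 (s) | No clear grade (s) | Width (ms) |
|---|---|---|---|
| 0.44 | 0.50 | none | 0 |
| 0.445 | 0.505 | 0.50 to <0.505 | 5 |
| 0.45 | 0.51 | 0.50 to <0.51 | 10 |
| 0.46 | 0.52 | 0.50 to <0.52 | 20 |
| 0.47 | 0.53 | 0.50 to <0.53 | 30 |

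Example: baseline 0.46 s, QTc 0.51 s, rise 0.05 s. Without symptoms this is Grade 3 and treatment stops. With symptoms it meets none of Grades 1 to 3.

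For a rise of 0.06 s or more, the grade turns on whether the word asymptomatic governs the second limb too. If it does not, the patient is Grade 3; if it does, there is again no grade. Below 0.50 s most symptomatic patients also lack a grade, but there, apart from that second limb, 8.5 asks at most for monitoring, so no stop is lost.

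Such baselines can enter the trial: 4.2 excludes a history of prolonged QT syndrome, but neither 4.1 nor 4.2 sets a QTc ceiling.

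**The case against.** The strongest reply is that 8.1 contains an obvious slip and 8.5 is the working rule. Section 1.3 uses the verb just as loosely ("In a Phase II randomized controlled trial which substituted Moxifloxacin with Ethambutol") while arguing that moxifloxacin can stand in for ethambutol. Table 4 and 8.5 both identify moxifloxacin as the QT-prolonging drug. A reader might infer that the protocol means to start moxifloxacin in control patients with a long QT; the documents do not support that, and the literal exposure in Step 1 shows only where the wording could act. That it is a slip stands. It still needs correcting.

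A second reply is that 8.5, with its graded criteria, is the more specific text and so governs. That is reasonable practice, but 8.1 is also about QT and is also mandatory, and no text gives precedence. It may be added that Grade 3 in 8.5 is not called permanent and that 8.3.3 leaves further TB treatment to the clinician, so treatment could be stopped and later resumed with ethambutol. The QTc text does not provide that sequence. At Grade 4, drug-attributed cases go to the national programme off study drugs, and the clash is firm.

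Third, on the grading gap, a reader might infer that a symptomatic patient would stay on moxifloxacin unless the investigator used discretion. That goes too far: 8.1 as intended has no grade or symptom limit and removes moxifloxacin on any evidence of prolongation. Grade 4 also gives its dysrhythmias only as examples, so an investigator may assign it. This objection stands. What is left unsettled is the grade itself and the full stop with hospital referral.

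Finally, it is tempting to call the missing continuation-phase ethambutol dose an error. Table 2 gives weight-banded doses within the four-drug tablet, and 6.1 points to national dosing guidelines, so there is a basis for dosing. That point, and the absence of a statement that the baseline ECG precedes the first dose, are missing detail only.

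**Conclusion.** The 8.1 QT action is wrong as written. Read as intended, it conflicts with 8.5 at Grades 3 and 4 on whether the other TB drugs continue with ethambutol, except where another illness or drug is the likely cause. About 165 patients are assigned the drug concerned. The documents give no rate of QTc prolongation, so no count of affected patients can be offered.

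The grading gap is real but secondary. It is 5 to 30 ms wide for baselines of 0.445 to 0.47 s, and absent at 0.44 s or below. It is wider only if the asymptomatic limit is read across both limbs of Grade 3.

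This rests on two assumptions: that the intended 8.1 action is the reverse of its wording, and that the general DAIDS grading table, which is not in the documents, does not fill the gap. The second cannot be checked, though 8.5 describes its QTc criteria as specific to this protocol. The correction should be made.

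**What to change.** 1. In 8.1, write that *ethambutol will be substituted for moxifloxacin*. Keep the QRS trigger in that sentence, since 8.5 has no QRS rule, and state that the 8.5 actions govern at Grades 3 and 4.
2. In 8.5, delete the asymptomatic limit from the Grade 3 cell, or state that symptomatic QTc of 0.50 s or more is at least Grade 3. Deletion also settles the scope of the second limb.

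Optional clarifications: give the ethambutol dose for a patient switched during the continuation phase, and say that the baseline ECG is recorded before the first dose.

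The cost is protocol wording, with no added visit or ECG. The downside is that some symptomatic patients would stop all study drugs by rule, where at present the full stop is left to judgement.
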